10.2. ENDPOINTS

10.2.1. Primary Endpoint

- Overall response rate (ORR) according to the RECIST.

10.2.2. Secondary Endpoints

Efficacy:

- Progression-free survival rate at four months (PFS4)
- Progression-free survival rate at six months (PFS6)
- Duration of response (DR).
- Progression-free survival (PFS).
- Overall survival (OS).

Safety profile:

- Clinical examinations.
- Vital signs analysis.
- Clinical assessment of AEs and SAEs.
- Changes in laboratory parameters (hematological and biochemical, including liver function tests).
- Reasons for study discontinuations.
- Any other analyses that may be considered necessary.

Others:

- Pharmacokinetic (PK) profile.
- Pharmacogenomic (PGx) profile.

10.3. STATISTICAL ANALYSIS

Continuous variables will be tabulated and presented with summary statistics (i.e., mean, standard deviation, median and range). Categorical variables will be summarized in frequency tables by means of counts and percentages.

10.3.1. Efficacy Analysis

All patients who have received at least four of the six infusions in the first two cycles (i.e., two infusions in each cycle, or three infusions in Cycle 1 and one infusion in Cycle 2), and who have at least one disease measurement recorded not less than six weeks after treatment onset, will be considered evaluable for efficacy. In addition, any eligible patient who receives at least two of three infusions in one treatment cycle and experiences disease progression or dies due to PD prior to response evaluation will be considered evaluable for the main endpoint (ORR) and will be categorized as an “early progression”.

Patients withdrawn due to toxicity without any tumor assessment after the start of study treatment will be considered as “treatment failures” and will not be replaced.

Patients withdrawn due to significant clinical deterioration of unknown reason, hypersensitivity reactions, refusal to continue on study for any reason or unrelated AEs without any tumor assessment after the start of study treatment will be considered not evaluable for efficacy and will have to be replaced.

Binomial estimates with exact 95% CIs will be calculated for the analysis of the main endpoint (ORR) and the secondary endpoints PFS4 and PFS6 rates.

Time-to-event endpoints (DR, PFS and OS) will be analyzed according to the Kaplan-Meier method.

If relevant, efficacy parameters *versus* baseline covariates will be analyzed and appropriate test will be used (i.e., the Fisher exact test for categorical variables, the log-rank test or Cox regression for time-to-event variables, etc.).

10.3.2. Safety Analysis

All patients who have received at least one total or partial infusion of PM00104 will be included in the safety analysis.

The AEs, SAEs, laboratory evaluations, deaths and the reason for study discontinuations will be analyzed.

All AEs and SAEs will be classified according to the NCI-CTCAE, v. 3.0, and will be coded using the MedDRA, v.10.0.

10.3.3. Pharmacokinetic Analysis

Pharmacokinetic parameters will be calculated using population methods, after pooling data from this study with data obtained during phase I studies.

10.3.4. Pharmacogenomic Analysis

The results of the PGx analyses conducted on the tumor tissue obtained at disease diagnosis and blood samples obtained prior to the first treatment administration will help to generate hypotheses for correlating the molecular parameters assessed in these samples with the clinical results of the treatment.

11. ADMINISTRATIVE SECTION

11.1. ETHICS

This clinical trial will be conducted in accordance with the ethical principles that have their origin in the World Medical Association (WMA) Declaration of Helsinki (see [Appendix 5. Declaration of Helsinki](#)) and will be consistent with Good Clinical Practice (GCP) guidelines and pertinent regulatory requirements.

The study personnel involved in conducting this trial will be qualified by education, training and experience to perform their respective task(s).

The study will be conducted in compliance with the protocol. The protocol, any amendments and the patient informed consent will receive IEC/IRB approval/favorable opinion prior to initiation, according to pertinent regulations.

The decision of the IEC/IRB concerning the conduct of the study will be made in writing to the Investigator, and a copy of this decision will be provided to the Sponsor before the beginning of the study.

The Investigator and/or the Sponsor is/are responsible for keeping the IEC/IRB informed of any significant new information about the study drug.

All protocol amendments will be agreed upon by the Sponsor and the Investigator.

Administrative changes of the protocol are minor corrections and/or clarifications that have no impact on the way the study is to be conducted.

11.2. MONITORING, AUDITING AND INSPECTING

The study will be monitored by regular site visits and telephone calls to the Investigator by the PharmaMar clinical trial monitor.

During site visits, the trial monitor should review original patient records, drug accountability records and document retention (study file). Additionally, the trial monitor should observe study procedures and will discuss any problems with the Investigator.

Adequate time for these visits should be allocated by the Investigator. The Investigator should also ensure that the monitor is given direct access [as per International Conference on Harmonization (ICH) Topic E6 (R1) Guideline for Good Clinical Practice, Sections 4.9.7 and 6.10] to source documents (i.e., hospital or private charts, original laboratory records, appointment books, etc.) of the patient which support data entered in the case report forms, as defined in the ICH Topic E6 (R1) Guideline for Good Clinical Practice, Sections 1.51 and 1.52.

Systems and procedures will be implemented to ensure the quality of every aspect of the trial.

During the course of the trial, the Clinical Quality Assurance Department of PharmaMar or external auditors contracted by the Sponsor may conduct an onsite audit visit (ICH Topic E6 (R1) Guideline for Good Clinical Practice, Section 1.6).

Participation in this trial implies acceptance of potential inspection by national or foreign health authorities.

11.3. PATIENT INFORMED CONSENT FORM

The rights, safety and well-being of the trial patients are the most important considerations and should prevail over interests of science and society.

The Informed Consent Forms will include all elements required by ICH, GCP and applicable regulatory requirements.

Prior to inclusion into the trial, the Investigator or a person designated by the Investigator must provide the patient with one copy of the Informed Consent Form for the clinical trial and one copy of the Informed Consent Form for the PGx substudy. Both copies must provide written fully information about the clinical trial and the PGx substudy in a language that is non-technical and easily understood. The Investigator should allow time necessary for the patient or his/her legally acceptable representative to inquire about the details of the clinical trial and the PGx substudy; then, both Informed Consent Forms must be freely signed and personally dated by the patient and by the person who conducted the informed consent discussion before the beginning of the study. The patient should receive a copy of both signed Informed Consent Forms and any other written information provided to study patients prior to participation in the trial.

During a patient's participation in the trial, any updates to the consent forms and any updates to the written information will be provided to him/her.

If there is a need to obtain new consent from the patients, the Investigator or a person designated by the Investigator should inform the patients of any new information relevant to the patients' willingness to continue participation in the study, before obtaining the written consent.

11.4. CONFIDENTIALITY / IDENTIFICATION OF PATIENTS

The collection and processing of personal data from the patients enrolled in this clinical trial will be limited to those data that are necessary to investigate the efficacy, safety, quality and usefulness of the study drug used in this trial.

It is the Investigator's responsibility that sufficient information on the identity of the patients will be retained.

The trial monitor, the Sponsor's auditor, the IECs/IRBs and the regulatory authorities should have direct access to all requested trial-related records, and agree to keep the identity of study patients confidential.

The data must be collected and processed with adequate precautions to ensure confidentiality and compliance with applicable data privacy protection laws and regulations.

Explicit consent for the processing of personal data will be obtained from the participating patient before data collection, and this consent should also address the transfer of the data to other entities and countries.

PharmaMar shall comply with the Directive 95/46/EEC of the European Parliament and of the Council of 24 October 1995 on the protection of individuals with regard to the processing of personal data and on the free movement of such data.

11.5. CASE REPORT FORMS

Case report forms (CRFs) will be used to record all data for each patient. It is the responsibility of the Investigator to ensure that the CRFs are properly and completely filled in. CRFs must be completed for all patients who have given their informed consent and have been enrolled into the study.

A patient's source documentation is the physician's patient records, and as such they should be maintained at the study site.

The data collected in the CRF will be entered into PharmaMar databases, which comply with the Spanish Act implementing the Directive 95/46/EC of the European Parliament and of the Council of 24 October 1995 on the protection of individuals with regard to the processing of personal data.

11.6. INSURANCE

The Sponsor will provide insurance or indemnity in accordance with applicable regulatory requirements.

11.7. RETENTION OF RECORDS

The Investigator/Institution should maintain trial documents according to Section 8 of the ICH Topic E6 (R1) Guideline for Good Clinical Practice and as required by applicable regulatory requirements.

Essential documents should be retained as per the aforementioned ICH guideline or for a longer period of time, if required by the applicable regulations.

11.8. USE OF INFORMATION AND PUBLICATIONS

Before the investigators of this study submit a paper or abstract for publication or otherwise publicly disclose information concerning the study drug or products, PharmaMar must be provided with at least 60 days to revise and approve the proposed publication or disclosure to ensure that confidential and proprietary data are protected.

If PharmaMar determines that patentable patient matter is disclosed in the proposed publication or disclosure, the publication or disclosure will be withheld for a period of time considered convenient. If the study is part of a multicenter study, the first publication of the study shall be made in conjunction with the presentation of a joint, multicenter publication of the study results with the investigators and the institutions from all appropriate sites that are contributing data, analysis and comments. However, if such a multicenter publication is not submitted within 12 months after conclusion, abandonment or termination of the study at all sites, the present study may be published individually in accordance with the procedure established above.

The order of the coauthors will reflect the relative contribution of each one to study development and analysis. In general, the first author will be the investigator who recruits the highest number of patients with information finally available for data

analysis. Relevant PharmaMar personnel who have fully participated in the study must be considered for co-authorship of the publication.

These analyses will include the use of transcriptional profiling technologies and other molecular biology techniques to identify and validate pharmacogenomic markers from pre-treatment tumor samples. These basal expression levels of these markers will be correlated with the patient's response outcome data. In addition, the experimental data will be analyzed with respect to duration of response, time to disease progression and overall survival.

The gene expression of selected DNA repair related genes and the determination of the genotype for the selected SNPs will be determined by qRT-PCR at the laboratory of Molecular Oncology of Pangaea Biotech, Barcelona, Spain. The DNA repair related protein expression analysis will be determined at the Molecular Pathology laboratory of CNIO (Centro Nacional de Investigaciones Oncológicas Madrid, Spain) by IHC techniques using the correspondent antibodies. GEP and IHC analysis will be determined at basal conditions; that is using the tumor tissue obtained at the diagnosis of the disease. SNP analysis will be performed on blood samples obtained before the treatment with PM00104.

All patients included in the study PM104-B-001-09 are eligible for the PGx studies. However, only those patients that voluntarily sign the Informed Consent for the Pharmacogenomic study will participate. The refusal for participation in the Pharmacogenomic study will not affect the participation in the associated clinical study.

2. Blood and Tumor Tissue Samples

PharmaMar will provide a "Guide for identification, packaging and shipment of Pharmacogenomic samples" detailing the procedures to follow for sample collection, labeling and shipment.

The ideal sample for gene mRNA expression analysis is paraffin-embedded tumor tissue obtained at the diagnosis of the disease because it is frequently conserved in the pathology archives and allows the determination of the mRNA expression analysis of selected genes by Quantitative RT-PCR.

Depending on the availability of the tissue blocks to be shipped outside the site, the investigator can choose between two options:

Option #1 (for sites that will be sending the paraffin-embedded tissue blocks): ship only the paraffin block to PharmaMar, at ambient temperature using the labeled zip-lock bag and the air-bag envelope provided. Fill the biopsy specimen number in the PGx Sample Collection Form. PharmaMar will take responsibility for processing the

tissue block and preparing the slides. The tissue block will be shipped back in 3-4 weeks after reception.

Option #2 (for sites that will not be sending paraffin blocks): mount the sample slices into the appropriate microscope slides. A detailed description of the procedure of cutting sections is provided in the “Guide for identification, packaging and shipment of Pharmacogenomic samples”. Number and characteristics of the paraffin embedded tissue samples required.

1.- RNA slices: five tissue slices 5 µm thick mounted in PEN Membrane Slides for microdissection of tumoral tissue to extract RNA.

2.- IHC slices: ten tissue slices 3 µm thick mounted in SuperFrost Slides for immunohistochemistry analysis.

Blood samples: 10 ml of patient’s peripheral blood in a 10 ml purple top tube containing EDTA as anticoagulant. Blood samples have to be stored frozen at least at –20°C until shipment.

3. Patient Samples Labeling and Shipment

The blocks or the slides and the tubes containing the samples are labelled with coded numbers (PGx code) to ensure the blindness of the study. Samples will be sent to PharmaMar stripped of all patient identifiers with the Investigator team holding the key that correlates the tumor sample with the response to PM00104 and all patient’s clinical data.

Sample shipments to PharmaMar will be performed every 6 months or 5 patients, whatever come first. PharmaMar will contact the investigator requesting the preparation of the shipment and will obtain the legal authorizations required for shipping biological samples (legal authorizations vary between countries of origin of the samples). The contact person in PharmaMar is [name] [name], [contact], [contact].

PharmaMar will cover all the expenses of the shipment and will provide all the shipment materials in advance.

PharmaMar is responsible for long-term storage of the samples and for the shipment to the genomics laboratories where the PGx analysis will be performed. Once tissue slices have been obtained, the tissue blocks will be returned to the pathology departments of origin 3-4 weeks after reception

The labeling and shipment of patient samples is described in more detail in the “Guide for identification, packaging and shipment of Pharmacogenomic samples”.

4. Methodology for Analysis

- a. Tumoral tissue microdissection: Those samples having large proportion of non-tumoral tissue need to be laser microdissected for isolation of the tumoral cells. Paraffin-embedded tissue slices need to be mounted on Pen Membrane microscope slides provided by PharmaMar. The tumoral tissue is laser captured under the microscope and separated for DNA/RNA extraction. If necessary, several tissue slices will be microdissected to obtain a minimum of 1 mm² of microdissected tumoral tissue that is required for the analysis.

- b. DNA/RNA isolation: DNA is isolated using a commercial kit (QIAmp® DNA blood Mini kit; Qiagen). Total RNA was recovered from formalin-fixed, paraffin-embedded surgical specimens using proteinase K digestion and phenol-chloroform extraction.
- c. Quantitation of mRNA expression will be analyzed by real-time quantitative reverse transcriptase PCR using the ABI Prism 7900HT Sequence Detection System (Applied Biosystems, Foster City, CA, USA) in a two-step process. In the reverse-transcription (RT) step, cDNA synthesized by reverse transcription from 1-100 ng of total RNA extracted from the samples using random primers. In the PCR step, PCR products are synthesized from cDNA samples using the TaqMan Universal PCR Master Mix. The PCR step employs the 5' nuclease assay, which produces a fluorescent signal proportional to the amount of amplified DNA produced in each PCR cycle. Finally, the initial relative amount of mRNA is determined by the Cycle Threshold method, using as control the control gene and the control samples. The mRNA expression levels are normalized to the B-actin expression in the same samples.
- d. Genotyping: genotyping of the single nucleotide polymorphisms is performed using the 5' nuclease allelic discrimination assay. The PrimerExpress program (Applied Biosystems) was used to design probes and primers for the analysis of each single nucleotide polymorphism. To avoid amplification of non-specific DNA all oligonucleotide sequences were checked in the BLAST Search program (available at <http://www.ncbi.nlm.nih.gov/LocusLink/BLAST/>). Each reaction mixture (25 µL) of polymerase chain reaction contained 50 ng of DNA, 900 nM of each forward and reverse primer, 300 nM of each allele specific probe and 12.5 µL of Taqman Universal PCR Master Mix (Applied Biosystems). Fluorescence in each sample well is measured each cycle before and after polymerase chain reaction using ABI Prism 7000 Sequence Detection System (Applied Biosystems). Data are analyzed using Allelic Discrimination Program (Applied Biosystems). To assure the accuracy of genotyping with the use of this method, 10 DNA samples will be randomly selected and subjected them to polymerase chain reaction and direct DNA sequencing in an ABI Prism 310 Sequence Detection System (Applied Biosystems).
- e. Generation of tissue-arrays (TMA): for characterization of IHC protein expression, we will construct a tissue-array containing the patient samples assembled as previously described (1). Briefly, two 1.5-mm-diameter cylinders of tissue are taken from representative areas of each archival paraffin block and arrayed into a new recipient paraffin block with a custom-built precision instrument (Beecher Instruments, [name]) according to the previously described method (2). Areas chosen for the cylinder core have high tumor cellularity. In order to evaluate the most active part of each primary tumor, the invasive border of the tumor in large lesions and all tumor cells in smaller samples are selected. In addition, normal tissues and three different cell lines with known cell-cycle alterations are placed adjacent to tumoral tissues to serve as internal controls and to ensure the quality of staining slides. Initial

sections are stained for hematoxylin and eosin to verify the histopathological findings.

- f. Immunohistochemistry: three-micrometer tissue sections from the TMA blocks are sectioned and applied to special immunohistochemistry coated slides (Dako). These slides are baked overnight in a 56°C oven. Sections are deparaffinized in xylene for 20 minutes, rehydrated through a graded ethanol series and washed with phosphate-buffered saline. Antigen retrieval is achieved by a 2-minute heat treatment in a pressure cooker, containing 1 l of 10 mM sodium citrate buffer, pH 6.5, that has been previously brought to the boil. Before staining, endogenous peroxidase activity is quenched with 1.5 % hydrogen peroxide in methanol for 10 min. Immunohistochemical staining is performed on these sections using adequate antibodies for detection of the selected proteins. After incubation, in the case of nuclear markers, immunodetection is performed with the LSAB Visualization System (Dako, Glostrup, Denmark) using 3,3'-diaminobenzidine chromogen as substrate, according to the manufacturer's instructions. In addition, whenever possible, cytoplasmic markers are visualized with the APAAP system (alkaline phosphatase anti-alkaline phosphatase, Dako, Glostrup, Denmark), using neofuchsin chromogen as substrate to rule out the possibility of a role of endogenous melanin in the observed reactivity. All sections are counterstained with hematoxylin. Negative controls are obtained by omitting the primary antibody.
- g. Scoring systems: immunostaining intensity is evaluated by two different pathologists and scored using uniform and clear cut-off criteria, in order to maintain the reproducibility of the method. Discrepancies are resolved by simultaneous re-evaluation. Briefly, the result of immunostaining is recorded as negative or positive, and low versus high expression, taking into account the expression in tumoral cells and the specific cut-off for each marker. As a general criterion, the cut-offs are selected in order to facilitate reproducibility, and when possible, to translate biological events.
- h. Statistics: clinical data and immunohistochemistry scoring are performed blind, and data are compiled only after all analyses are completed. Fisher's exact test is used to test whether a specific protein-expression profile is associated with the clinical outcome after Zalypsis[®] treatment. Significance is concluded for values of $p < 0.05$. The prognosis value of markers will be explored for objective clinical response, progression free survival and survival. In each case, a multivariate model is developed by backwards elimination, starting with all markers with a p-value lower than 0.10 in the univariate analysis. Hazard ratios will be calculated with the univariate Cox model, and comparison between Kaplan-Meier survival and progression free survival curves will be performed with the log-rank test. All tests of statistical significance are two-sided, and significance is set at 0.05 except in multiple comparisons, where it is set at 0.017 in accordance with the Bonferroni correction.

References:

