10.1. SAMPLE SIZE

In this phase II trial, efficacy of PM00104 will be evaluated in two different groups of patients with endometrial or cervical cancer. A total of 62 evaluable patients are expected to participate in this clinical trial:

- 30 patients in Group 1 (endometrial cancer), and
- 32 patients in Group 2 (cervical cancer).

A different ORR is to be expected depending on the type of cancer. Thus, patients with endometrial cancer may achieve higher response rates with second-line single-agent therapies (around 25-30%) (6) than patients with cervical cancer (around 15-20%) (79, 80). Therefore, the sample size has been calculated in each group using a similar design (based on the Simon two-stage design for phase II trials) (81), but using different figures for null and alternative hypotheses.

Group 1 (endometrial cancer): patients with endometrial cancer who have received one previous systemic chemotherapy line for advanced/metastatic disease (excluding chemosensitizing chemotherapy); prior hormone therapy and biological therapy are allowed.

A Simon two-stage design will be adopted in this group to test the null hypothesis that the ORR by RECIST is $\leq 10\%$ *versus* the alternative that $\text{ORR} \geq 30\%$ (two-sided test; $\alpha=0.1$ and $\beta=0.1$). A maximum of 30 evaluable patients will be included in this group. In a first stage, 10 evaluable patients will be recruited. If one or more (≥ 1) patients achieve an objective response, the accrual in this group will be expanded with 20 additional evaluable patients. If the total number of patients with objective response is 6 or more (≥ 6) in 30 evaluable patients (i.e., an ORR in the whole study of at least 20%), the null hypothesis will be rejected and PM00104 will be considered for further clinical development in endometrial cancer.

Group 2 (cervical cancer): patients with cervical cancer who have received one previous systemic chemotherapy line for advanced/metastatic disease (excluding chemosensitizing chemotherapy); prior hormone therapy and biological therapy are allowed.

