6.1 Sample size determination

In this phase II trial, efficacy of PM00104 will be evaluated in two different groups of patients with endometrial or cervical cancer.

Group 1 (endometrial cancer): A Simon two-stage design will be adopted in this group to test the null hypothesis that the ORR by RECIST is $\leq 10\%$ versus the alternative that ORR $\geq 30\%$ (two-sided test; $\alpha=0.1$ and $\beta=0.1$).

A maximum of 30 evaluable patients will be included in this group. In a first stage, 10 evaluable patients will be recruited. If one or more (≥ 1) patients achieve an objective response, the accrual in this group will be expanded with 20 additional evaluable patients.

If the total number of patients with objective response is 6 or more (≥ 6) in 30 evaluable patients (i.e., an ORR in the whole study of at least 20%), the null hypothesis will be rejected and PM00104 will be considered for further clinical development in endometrial cancer.

Group 2 (cervical cancer): Also a Simon two-stage design where the null hypothesis ORR by RECIST is $\leq 5\%$ vs. ORR $\geq 20\%$ (two-sided test; $\alpha=0.1$ and $\beta=0.1$).

A maximum of 32 evaluable patients will be included in this group. In a first stage, 18 evaluable patients will be recruited. If one or more (≥ 1) patients achieve an objective response, the accrual in this group will be expanded with 14 additional evaluable patients.

If the total number of patients with objective response is 4 or more (≥ 4) in 32 evaluable patients (i.e., an ORR in the whole study of at least 12.5%), the null hypothesis will be rejected and PM00104 will be considered for further clinical development in cervical cancer.

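### The pharmacogenomic marker tests specify no stratification by tumour group, so if they are run across both cancers a marker that only tracks tumour type can look predictive of response

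*Protocol*

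**What the plan says.** Appendix 1, item 4h, is the only statement of pharmacogenomic (PGx) statistical method in the two documents. Fisher's exact test "is used to test whether a specific protein-expression profile is associated with the clinical outcome". For time-to-event outcomes, "Hazard ratios will be calculated with the univariate Cox model", and survival curves are compared by log-rank. A multivariate model is then reduced by backward elimination, and its candidates are the markers with univariate p below 0.10. Tests are two-sided at 0.05, or 0.017 for multiple comparisons. Tumour group is not a stratum, covariate or subgroup in any of these steps, and Protocol 10.3.4 adds none.

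Appendix 1, item 1, makes every trial patient eligible, so endometrial and cervical patients can both enter. Protocol 10.1 explains the separate designs with the sentence "A different ORR is to be expected depending on the type of cancer" and gives about 25-30% for endometrial and 15-20% for cervical cancer.

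The SAP duplicates its tables, listings and figures by group, and it considers pooling only for safety (7.5 and the note before its Appendix I). SAP section 8 places the PGx analysis in a separate document, so the duplication rule does not reach it.

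**The concern.** Suppose a marker is common in one cancer and rare in the other. Suppose also that one cancer responds more often, for reasons unrelated to the marker. Marker-positive patients will then respond more often in the combined data even if the marker does nothing within either cancer. An ordinary Fisher test, a univariate Cox model or an unstratified log-rank test cannot separate the two explanations. The markers-only multivariate model cannot either, because tumour group is never offered to it.

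The substudy aims to find, and according to Protocol 8.4 also to validate, markers that could identify patients who benefit. A false lead of this kind would report tumour type as drug sensitivity. It is a bias, not a multiplicity problem, so a stricter significance level makes it less frequent without removing it.

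**Working it through.** **Figures stated in the plan.** The documents give no power for the PGx tests. The response rates come from the two Simon designs, which reproduce by exact two-stage binomial sums:

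- Group 1 (10 then 20 patients, at least 6 of 30, 10% vs 30%): one-sided alpha 0.069, power 0.907.
- Group 2 (18 then 14 patients, at least 4 of 32, 5% vs 20%): one-sided alpha 0.072, power 0.901.
- The PGx multiple-comparison level is 0.05/3 = 0.0167, as stated (0.017).

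**Inputs**

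- Group sizes 30 and 32 (Protocol 10.1). This is an upper limit, because the substudy takes only U.S. samples from consenting patients with tissue.
- Response rates within the ranges of Protocol 10.1: 30% vs 20%, 27.5% vs 17.5% (midpoints) and 30% vs 15% (widest gap). The pairing 30% vs 5% (Group 1 alternative, Group 2 null) is an extreme case.
- Marker prevalence by cancer is not in the documents. Assumed: 50/50 (unrelated to tumour type), 70/30 and 80/20.
- U.S. subset size is not in the documents. Assumed for illustration: 15+16.

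**How the spurious association arises (80/20, 30+32).** Expected marker-positive patients: 0.8×30 = 24 endometrial and 0.2×32 = 6.4 cervical. Expected marker-negative: 6 and 25.6.

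- 30% vs 20%: positives respond at (24×0.30 + 6.4×0.20)/30.4 = 27.9%, negatives at (6×0.30 + 25.6×0.20)/31.6 = 21.9%. Odds ratio 1.38.
- 30% vs 15%: 26.8% against 17.8%. Odds ratio 1.69.
- 30% vs 5%: 24.7% against 9.7%. Odds ratio 3.04.

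The true odds ratio within each cancer is 1 in all three cases.

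**False-positive rate for response.** 20,000 simulated trials per row, no marker effect within either cancer. The stratified test is an exact conditional test on the sum over the two tumour strata.

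| N | ORR | Prevalence | Pooled Fisher, p<0.05 | Pooled Fisher, p<0.017 | Stratified, p<0.05 |
|---|---|---|---|---|---|
| 30+32 | 30/20 | 50/50 | 0.03 | 0.01 | 0.03 |
| 30+32 | 30/20 | 70/30 | 0.04 | 0.01 | 0.03 |
| 30+32 | 30/20 | 80/20 | 0.06 | 0.03 | 0.03 |
| 30+32 | 27.5/17.5 | 80/20 | 0.06 | 0.02 | 0.03 |
| 30+32 | 30/15 | 70/30 | 0.07 | 0.03 | 0.03 |
| 30+32 | 30/15 | 80/20 | 0.10 | 0.04 | 0.03 |
| 30+32 | 30/5 | 80/20 | 0.28 | 0.15 | 0.03 |
| 15+16 | 30/20 | 80/20 | 0.04 | 0.01 | 0.02 |
| 15+16 | 30/15 | 80/20 | 0.06 | 0.02 | 0.02 |
| 15+16 | 30/5 | 80/20 | 0.13 | 0.04 | 0.02 |

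The right baseline is about 0.03, not 0.05, because Fisher's test is conservative at these sizes. A marker unrelated to tumour type shows no inflation.

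**Upper bound.** If the marker coincides with tumour type, exact enumeration of pooled Fisher with 30+32 patients gives 0.116 (30% vs 20%), 0.124 (27.5% vs 17.5%) and 0.248 (30% vs 15%). A stratified test then has no within-cancer contrast and cannot flag the marker.

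**Time-to-event outcomes.** Protocol 1.4 gives second-line PFS of 2 months in both cancers, so these figures imply no PFS bias. It gives OS of 6-8 months in endometrial and 6 months in cervical cancer. For a marker equal to tumour type, with 62 deaths and medians of 8 vs 6 months (hazard ratio 0.75), the normal approximation is z = √(62×30×32/62²)×|ln 0.75| = 3.935×0.288 = 1.13. The chance of p<0.05 is then about 0.20. It is about 0.09 at 7 vs 6 months and 0.05 at 6 vs 6.

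**The case against.** The strongest reply is that the plan never says the groups will be pooled. A reader might infer from 4h that the tests combine them, but shared eligibility is not a pooled test. The efficacy design is by group throughout, and the separate PGx document may stratify. This stands, and it limits the point to saying that no stratification is specified. It does not dispose of the point, because 4h is the method the protocol commits to and the SAP's by-group rule stops at its own tables.

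A reader might also take 0.28 as the expected size, reasoning that the trial has two groups because the drug may work in only one. The documents do not say that. Protocol 10.1 gives differing expected response rates as the reason. In the 30% vs 5% case Group 2 would also stop after 18 patients with probability 0.95^18 = 0.40, so 32 cervical patients would often not be available.

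The U.S.-only restriction further reduces the effect. With 15+16 patients and an 80/20 marker, the pooled rate is 0.04 to 0.06 within the protocol's expected ranges, close to nominal although still two to three times the stratified rate. Extending the claim to PFS is not supported, given the equal 2-month figures.

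Finally, Protocol 2.2 calls these analyses exploratory and hypothesis-generating, and no trial decision rests on them. That lowers the stakes. Protocol 8.4 also speaks of validating markers, so it does not remove them.

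**Conclusion.** The point holds as a minor one. Item 4h specifies no stratification or adjustment by tumour group for a substudy open to two cancers that the protocol expects to respond differently. If the tests are run across both groups as written, a null marker with 80/20 prevalence is flagged at p<0.05 with probability about 0.06 to 0.10 with all 62 patients, against 0.03 when stratified. The effect is smaller in a plausible U.S. subset and absent for markers unrelated to tumour type.

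These sizes rest on assumed prevalences, an unknown substudy size and the response ranges in Protocol 10.1. The bias is supported for response, and for OS only if endometrial survival exceeds 6 months. It would be wrong to conclude that the plan pools the groups, that inflation near 0.28 is to be expected, or that PFS is affected.

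**What to change.** In Appendix 1, item 4h, and in the separate PGx plan, state that every marker-outcome test is stratified by tumour group: an exact stratified conditional test for response, and stratified log-rank and Cox models for time-to-event outcomes. Keep tumour group in the multivariate models throughout, outside the backward elimination. Show the within-group tables beside each combined result.

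The cost is a sentence or two of text and a stratum statement in the program, since tumour group is known for every patient. Power falls when a marker nearly coincides with tumour type, but there the data cannot separate marker from tumour in any case. When the marker is unrelated to tumour type, the simulated false-positive rates of the two tests are practically the same. If the PGx plan already analyses each group separately, one sentence in 4h saying so is enough.
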